## Research Design and Methods

We propose to determine the effects of midodrine, administered in a randomized, double blind, placebo-controlled, outpatient trial to normalize BP over a 30-day period, on CBF, cognitive function, mood and QOL. Our primary objective is to generate pilot data describing the effect size of change in CBF, cognitive test score, mood and QOL following sustained elevation in BP, to normal levels, in hypotensive individuals with SCI.

Approximately 50 subjects with SCI will be screened for study eligibility. We anticipate that approximately 40 of the subjects screened will be eligible and will undergo a 4-hour laboratory dose-effect trial. Once dose has been determined subjects will be randomized by IVAN (Interactive Touch Tone Randomization System) to receive either midodrine or placebo for the 30-day out-patient drug treatment intervention. Randomization will occur in a double-blinded manner, and individuals that use an abdominal binder regularly will be stratified equally as will those with a positive history of traumatic brain injury (TBI). Our recruitment target is 20 subjects per randomization category. We estimate approximately 10% attrition during the 30-day out-patient treatment protocol; as such, complete data will be available in ~36 subjects. Study medication and placebo will be distributed by the James J Peters VAMC Pharmacy Service. The study is proposed to be completed in two years. Total enrollment will be accomplished within 18 months of obtaining full IRB approval, which should be complete within 6 months of funding, and subject participation is estimated to last about 6-8 weeks.

**Eligibility Criteria – Inclusion Criteria:** (1) males and non pregnant females; (2) 18 – 65 years of age; (3) chronic SCI ( $\geq 1$  year post injury); (4) ability to provide informed consent; (5) laboratory or clinical evidence of hypotension (WHO criteria - SBP  $\leq 110$  mmHg in males and  $\leq 100$  mmHg in females). **Exclusion Criteria:** (1) SBP  $> 110$  mmHg for males and  $> 100$  mmHg for females (2) documented history of: (a) coronary artery disease, (b) stroke, (c) diabetes mellitus, (d) current pregnancy or lactation, (e) cardiac arrhythmias; (f) significant systemic, hepatic, cardiac or renal illness, (g) suspected malignancy, (h) neurological disease other

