**Dose Determination Visit** – The dose determination visit will be scheduled to begin no less than 2 days and no more than 14 days after completion of the screening visit. Our preliminary data suggest that midodrine 10 mg normalized seated SBP during a 4-hour laboratory observation in 55% of the patients with SCI tested. Therefore, it is anticipated that the 10 mg dose of midodrine will be adequate to normalize seated BP in about half of our sample. However, we appreciate that some subjects with SCI will not respond adequately to 10 mg dose (our preliminary data suggest that 28% may require a higher dose), and others may have a hypertensive response ( $>139$  mmHg: 17%, based on preliminary evidence). Eligible participants will be administered midodrine 10 mg, open-label, and BP will be monitored for 4-hours; individuals with an average 4-hour seated SBP between 111-135 mmHg will be randomized to receive 10 mg midodrine (or placebo) during the Treatment Phase. However in those with inadequate responses to 10 mg, a second open-label trial will be carried out to determine 4-hour seated SBP responses at a higher dose (15 mg) for individuals with an average SBP  $\leq$  110 mmHg, and at a lower dose (5 mg) for those with an average SBP  $> 135$  mmHg. Individuals that respond to midodrine, at any of the doses tested, with two or more consecutive BP observations of  $>135/85$  mmHg, will be excluded from the treatment phase of the investigation. Brachial BP will be recorded at 15 minute intervals and these visits will take about 5 hours.

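### The planned flow allows no loss at dose determination, although an exclusion operates there, and as written that exclusion removes most subjects meant for the 5 mg test

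*Combined protocol and SAP*

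**What the plan says.** The subject flow is in the second paragraph of Research Design and Methods. About 50 are to be screened. Of these, "We anticipate that approximately 40 of the subjects screened will be eligible and will undergo a 4-hour laboratory dose-effect trial". Randomisation follows once the dose is known: "Our recruitment target is 20 subjects per randomization category", which is 40 in all. The only later loss is in the outpatient phase: "We estimate approximately 10% attrition during the 30-day out-patient treatment protocol; as such, complete data will be available in ~36 subjects".

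The Dose Determination Visit paragraph of the same section sets the rules between dose testing and randomisation. All eligible subjects first receive 10 mg open-label.

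- Average SBP in the target band: "individuals with an average 4-hour seated SBP between 111-135 mmHg will be randomized" to 10 mg or placebo.
- Average SBP at or below 110 mmHg: a second test at 15 mg.
- Average SBP above 135 mmHg: a second test, "and at a lower dose (5 mg) for those with an average SBP" above that value.
- Exclusion: "Individuals that respond to midodrine, at any of the doses tested, with two or more consecutive BP observations of" >135/85 mmHg leave before the treatment phase.

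The paragraph cites preliminary data in which 55% normalised on 10 mg and 28% might need more. It adds that "others may have a hypertensive response", defined as >139 mmHg and put at 17%. On the measurement schedule: "Brachial BP will be recorded at 15 minute intervals and these visits will take about 5 hours".

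**The concern.** There are two linked problems.

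First, the same 40 people are both dose-tested and randomised, yet an exclusion lies between those steps. The fall from 50 to 40 cannot absorb it, because the 40 are those who undergo dose testing. The 10% cannot absorb it either, because it belongs to the 30-day outpatient phase. These are the only size figures in a pilot meant to describe effect sizes for a larger trial.

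Second, the titration rules conflict. A subject averaging SBP above 135 mmHg on 10 mg is sent to 5 mg, but the exclusion covers every dose tested and so includes the 10 mg readings. Someone with that average will usually have two adjacent high readings. Two staff members following the paragraph could treat the same subject differently, one offering 5 mg and the other excluding. The exclusion can also catch subjects averaging 111–135 mmHg, whose randomisation is stated without condition. Nor does the plan say whether >135/85 requires both limits to be exceeded or either one.

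**Working it through.** **1. The plan's own figure.** Inputs, all from Research Design and Methods: 20 per arm and 10% outpatient attrition. 2 × 20 = 40, and 40 × (1 − 0.10) = 36. The figure reproduces exactly, with zero loss between dose testing and randomisation.

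**2. The flow with a loss L at dose determination.** From 40 dose-tested, randomised = 40(1 − L) and complete = 0.9 × 40(1 − L) = 36(1 − L). To keep 40 randomised, the number dose-tested is 40/(1 − L). The number screened is that divided by 40/50 = 0.80. L is not in the documents, so two illustrations follow:

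| L | Randomised from 40 | Complete | Dose-tested to keep 40 | Screened to keep 40 |
|---|---|---|---|---|
| 5% | 38.0 | 34.2 | 42.1, so 43 | 43/0.8 = 53.75, so 54 |
| 30% | 28.0 | 25.2 | 57.1, so 58 | 58/0.8 = 72.5, so 73 |

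**3. The 5 mg step, by reasoning.** Four hours at 15-minute intervals gives about 16 readings. If SBP alone counts, a subject avoids exclusion only if no two adjacent readings exceed 135 mmHg. At most 8 of the 16 can then be high. The average must still exceed 135 mmHg with at least half the readings at or below it, which is rare.

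**4. The 5 mg step, by simulation.** Subject averages on 10 mg were drawn from the 14-subject pilot reported under Preliminary Studies (119±18/76±14 mmHg). That may not be the sample behind the 17%. The following inputs are assumed and not in the documents: within-subject SBP SD of 4–12 mmHg, DBP SD of 0.5–0.7 of that, lag-1 correlation of 0 or 0.5, SBP–DBP correlation of 0.4–0.8, and a flat or peaked post-dose profile (96 settings). A second set used SBP SD of 5–12 mmHg and SBP–DBP correlation of 0.5–0.9.

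- Average SBP >135 mmHg on 10 mg: excluded in at least 99.8% if SBP alone or either limit counts. If both limits must be exceeded, 51–94% in the first set and 61–96% in the second.
- Average 111–135 mmHg: excluded in about 10–50% on SBP alone and about 4–35% if both limits are required.
- All subjects, on 10 mg alone: roughly 11–44% across the SBP-alone and both-limits readings. If either limit suffices, the second set gave 36–62%.

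**5. Precision.** If recruitment stopped at 40 dose-tested, confidence intervals would widen by about 1/√(1 − L). That is 1/√0.95 = 1.03 at 5% and 1/√0.70 = 1.20 at 30%. As a direct check, the 95% half-width for a difference in means is t × √(2/n) in SD units: 0.677 at 18 per arm and 0.748 at 15, about 10% wider.

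**The case against.** The strongest reply is that nothing is miscalculated and nothing says recruitment stops at 40 dose-tested. The 50 and 40 are approximate, and the firm item is 20 per arm. If subjects are lost at dose testing, the site can screen more until the target is met. This stands. The loss may fall on screening workload and the 18-month enrolment window, not on the number completing. It does not rescue the plan, because the stated screening and dose-testing numbers would then be too low.

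A second reply is that the authors evidently meant to keep subjects who go to 5 mg, so the exclusion was intended for the final dose only. That may be the intent, but the text applies the rule at any dose tested. Even on that reading, some loss at the final dose remains.

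A third reply is that the exclusion precedes randomisation, so it cannot bias the comparison with placebo, and that it errs towards safety. Both points are right and limit the consequence.

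Three stronger readings are not supported:

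- A reader might take the 17% as the loss and conclude that 33 are randomised and 30 complete (40 × 0.83 = 33.2; × 0.9 = 29.9). The 17% is for a >139 mmHg response, is given without a denominator, and matches neither the 5 mg trigger nor the exclusion. Using it also assigns no loss to the 111–135 mmHg group.
- A reader might say the 5 mg step is never or seldom used. If both limits must be exceeded, the first set of assumptions leaves 6–49% of those subjects available for it.
- A reader might infer an underpowered trial. No power is claimed.

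**Conclusion.** The concern holds in two parts. The flow of about 50, 40, 40 and ~36 is attainable only with no loss at a step where the protocol itself excludes subjects. That conclusion comes from the text and needs no model. As written, the exclusion also removes most subjects averaging SBP >135 mmHg on 10 mg before their 5 mg test. On SBP alone or either limit the removal is close to total and depends little on assumptions. On both limits it is about half to nine-tenths, and that range rests on assumed within-subject variability and SBP–DBP correlation.

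The size of the overall loss is unknown. The simulated 11–44% on 10 mg alone shows that it need not be small, but it is not an estimate to plan on. The statistical consequence is modest: intervals about 3–20% wider for losses of 5–30% if recruitment is not extended, or more screening if it is. The unclear handling of subjects at dose determination is the more important reason to amend the text.

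**What to change.** In the Dose Determination Visit paragraph:

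1. State whether >135/85 mmHg means both limits or either one.
2. Make the rules agree. Either apply the two-reading exclusion only at the dose to be carried forward, or keep it at any dose and delete the 5 mg step. This is a clinical safety decision, and the first choice needs safety agreement to re-dose after a hypertensive response.
3. Make randomisation of subjects averaging 111–135 mmHg conditional on not meeting the exclusion.

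In Research Design and Methods, state an assumed dose-determination loss L that covers every group under the chosen rule. This includes subjects still at or below 110 mmHg on 15 mg, for whom no outcome is given. Then restate the counts as 40(1 − L) randomised and 36(1 − L) complete, for example 38 and 34 at 5%, or 28 and 25 at 30%. Alternatively, keep 40 randomised and state the larger numbers: 43 dose-tested and 54 screened at 5%, or 58 and 73 at 30%. Counts built on the 17% should not be used as the replacement.

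The rule changes and restated counts cost only wording, at the price of a less favourable completer figure. Keeping 40 randomised costs 3 to 18 more dose tests (43 − 40; 58 − 40) and 4 to 23 more screenings (54 − 50; 73 − 50) over that range, within the 18-month enrolment window.

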about 60 minutes to complete and HR, BP, and CBF will be monitored and recorded during this testing. After the NP battery is complete, subjects will be asked to answer questions related to how BPD impacts their mood and QOL (Appendix 8); these short form questionnaires were developed for use in the SCI population and will take about 15-minutes to complete. In addition, to scales developed for use in the SCI population, because fatigue was ranked highest in terms of the adverse impact of hypotension on QOL by subjects with SCI from our focus group sessions (Figure 4), we will assess fatigue specifically using the PROMIS short form and the fatigue severity scale (Appendix 8). Finally, subjects will be equipped with a 24-hour BP monitor, and will be sent home with a log to record their activities of daily living (ADL) in association with the BP recordings (Appendix 9). In addition, subjects will be sent home with a 24-hour urine collection contained and will be asked to empty their leg bag, or to urinate into this contained at each voiding for a 24-hour period to assess hydration status. Post-randomization testing will be scheduled for approximately  $30\pm3$  days after randomization and, prior to returning to the laboratory, subjects will be asked to take their morning dose of the study medication. These visits will take about 4 hours.

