**Treatment Phase** –After pre-randomization testing, subjects will be randomized to either midodrine (at the individually effective dose) or matching placebo and will be sent home with a one-month ( $30\pm3$  day) supply. Subjects will be asked to take the study medication three times per day, at approximately 8 am, 12 noon and 4 pm; however, each patient will establish his/her daily regimen with [name] based on their individual sleep/wake schedules and ADLs. Subjects will be asked to keep a log of the time of day each dose was taken along with their BP and any adverse events (Appendix 10). Three BP values will be recorded and uploaded directly to [www.HealthVault.com](http://www.HealthVault.com) at the time of dosing and 1 hour after taking each daily dose (total of 18 BP entries daily). Only study investigators will have access to; this website, which will be password protected and the data will be stored behind the VA firewall. Study investigators will review daily BP entries and will contact the subject if data are missing or if there is evidence of a hypertensive episode. Subjects will be asked to report, immediately (within 1 hour), any significant AE, and study investigators will contact each subject weekly to discuss study specific information and general health and wellbeing. If an individual develops a fever or any other symptom of an acute illness or infection they will be taken off study medication and discontinued from participation and will be encouraged to visit their primary care physician for an evaluation. If after treatment of the illness or infection the subject is cleared for participation by the treating physician he/she may resume participation beginning with pre-randomization testing.

**Interim Visit** : Subjects will be asked to return to the laboratory approximately 10 days after randomization, in the late morning or early afternoon, after taking their scheduled daily dose for assessment of BP, HR and CBF and AE reporting. This visit will take about 2 hours.

**Follow -up Visit** – A follow-up visit will be scheduled 7 to 10 days after completion of the Treatment Phase to collect information on any AE(s) experienced after discontinuation of study medication and for a final laboratory assessment of HR, BP and CBF. This visit will take about 2 hours.

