#### **Study Objective s:**

Based on our pilot data we believe that the proportion of individuals classified as normotensive will be increased after 30-days of treatment with midodrine compared to those treated with placebo. We plan to classify individuals as normotensive if SBP is within the target range of 111-139 mmHg for  $\geq 50\%$  of the 24-hour observation (i.e., about 60 BP recordings) during the post-treatment period and the post-treatment relative risk of hypotension in the midodrine group versus placebo group will be assessed. Relative risk will be

determined by casting raw data into simple counts in a 2x2 contingency table, from which the proportion of cases that are classified as hypotensive in the midodrine group will be divided by the proportion of hypotensive cases in the placebo group. The 95% confidence interval for the relative risk value will be constructed, as described by Newcombe and Altman. In addition, clinical relevance will be quantified by calculating the number needed to treat (NNT) from the relative risk calculation as follows:  $NNT = 1 / (\text{hypotension rate in midodrine group} - \text{hypotension rate in placebo group})$ .

We hypothesize that, during a typical 24-hour day, the proportion of SBP observations within the target range of 111-139 mmHg will be increased after treatment with midodrine compared to placebo, after controlling for the baseline proportion. We anticipate that about >50% of the subjects randomized to midodrine will have normal 24-hour SBP after 30-days of treatment. In contrast we expect < 25% of individuals randomized to receive placebo to have normal 24-hour SBP after the 30-day intervention. If our postulated values are accurate, the relative risk for hypotension for the subjects on midodrine would be ~0.67, which represents about a 33% reduction in the rate of hypotension in subjects treated with midodrine compared to those randomized to placebo. The resulting NNT is ~ 4, which suggests that about 4 subjects with SCI would need to be treated with midodrine to normalize BP in one subject.

We will then determine the effect of increasing SBP to normal levels on the following outcome parameters:

Cerebral Blood Flow:

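### The plan does not say whether study medication is taken during the post-treatment 24-hour BP recording, so the 24-hour BP endpoint can be recorded mostly off drug

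*Combined protocol and SAP*

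**What the plan says.** All of this is in the combined protocol and SAP.

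- **Visit date** (Research Design and Methods, Pre- and Post-Treatment Visits): "Post-randomization testing will be scheduled for approximately $30\pm3$ days after randomization".
- **Supply** (Treatment Phase): each subject "will be sent home with a one-month ( $30\pm3$ day) supply". No surplus is stated.
- **Dose on the visit day** (Pre- and Post-Treatment Visits): "prior to returning to the laboratory, subjects will be asked to take their morning dose of the study medication". The later doses that day, and those of the next day, are not mentioned.
- **Standing schedule** (Treatment Phase): "three times per day, at approximately 8 am, 12 noon and 4 pm", with times adjusted to each subject's routine.
- **Order of the visit** (Pre- and Post-Treatment Visits): arrival is between 10 AM and 1 PM and the visit lasts about 4 hours. As the closing steps "subjects will be equipped with a 24-hour BP monitor", receive the activity log and urine container, and go home.
- **Endpoint** (Study Objectives): a subject is normotensive if SBP is 111-139 mmHg for at least 50% of the 24-hour observation, about 60 readings, "during the post-treatment period". The relative risk and NNT use this classification. A further hypothesis compares the proportion of readings in range between arms.

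**The concern.** The supply and the visit have the same nominal length, and the monitor goes on only when the visit is over. The 24-hour recording therefore runs into the day after the nominal supply is used up, and nothing says what subjects take during it. Subjects who follow the text could stop after the morning dose, finish the visit-day doses, or carry on as usual. The recording measures something different in each case.

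The 24-hour endpoint is how the plan shows that BP was normalized. The stated purpose is to supply convincing preliminary data for a large multi-site trial. If drug effect has worn off for most of the recording, the midodrine arm will resemble placebo on this measure even if BP was well controlled for the preceding 30 days.

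**Working it through.** **1. The plan's own figures.** Taking the expected normotensive proportions as 50% (midodrine) and 25% (placebo), the hypotension rates are 0.50 and 0.75.

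- RR = 0.50 / 0.75 = 0.67, as stated.
- NNT = 1 / |0.50 − 0.75| = 4, as stated (the printed formula, without the absolute value, gives −4).

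**2. When the recording starts.** Start = arrival + visit length = 10:00 + 4 h to 13:00 + 4 h = 14:00 to 17:00.

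- After an 08:00 dose the gap is 6 to 9 h. For a morning dose anywhere from 06:00 to 10:00 it is 4 to 11 h.
- A noon dose, if taken, is 2 to 5 h before the start.
- A 16:00 dose, if taken, falls between 2 h after the start and 1 h before it.

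**3. Supply against visit.** The nominal difference is 30 − 30 = 0 days. If the two ±3-day ranges vary independently, it runs from 27 − 33 = −6 to 33 − 27 = +6 days.

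**4. Share of the recording within a fixed time of a dose.** The documents give no duration of effect. I assume 4 h, the length of the observation in the Dose Determination Visit, and show 3 h and 6 h as a range. Dose times are 08:00, 12:00 and 16:00.

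| Doses taken | 4-h window | 3-6 h range |
|---|---|---|
| Morning dose only | 0 of 24 h (0%) | 0% |
| All three on the visit day, none the next day | 3-6 h (12.5-25%) | 2-8 h (8-33%) |
| Standing schedule continued | 12 h (50%) | 9-14 h (37.5-58%) |

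- Row 1: with 4 h, cover ends at 12:00; with 6 h, it ends at 14:00. Both are at or before the earliest start.
- Row 2: with 4 h, cover ends at 20:00, so 20 − 14 = 6 h or 20 − 17 = 3 h remain.
- Row 3: with 4 h, cover is 3 × 4 = 12 h in any 24. With 3 h it is 3 × 3 = 9 h. With 6 h the windows overlap into 08:00-22:00, or 14 h.

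**5. Effect on the planned result, as an illustration.** Assume an off-drug recording looks like placebo, and that a fraction f of the midodrine arm is recorded that way. The hypotension rate in that arm is then 0.50(1 − f) + 0.75f.

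- f = 0: RR 0.67, NNT 4.
- f = 0.5: rate 0.625, RR = 0.625 / 0.75 = 0.83, NNT = 1 / 0.125 = 8.
- f = 1: rate 0.75, RR = 1, NNT undefined.

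The value of f cannot be known from the documents.

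**The case against.** The strongest reply is that this is a gap in wording and that the sensible reading keeps subjects on drug. Much of it stands.

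- **Dosing is not said to stop.** A reader might infer that treatment ends at the visit and the recording is off drug by design. No section says so. The match between supply and visit is between nominal durations, each with a tolerance. The three-times-daily schedule has no visit-day exception, and the morning-dose sentence can be read as a reminder not to skip that dose.
- **The word post-treatment proves little.** It is also the name of the visit and of the analysis time point, and Study Objectives describes the result as following 30 days of treatment.
- **The exact-cut-off argument is weak.** A reader might infer that three doses cover exactly half the day and so only just reach the 50% criterion. That takes an observation length for a duration of effect and assumes undosed hours are out of range. The criterion also counts readings, whose spacing is not given, rather than hours.
- **The study would not be uninterpretable.** A reader might infer that a null result could never be explained. Subjects log each dose time and record home BP at dosing and 1 hour later. The interim visit measures BP and CBF after a dose, and the day-30 visit records BP and CBF together at rest and during cognitive testing. Arrival is 2 to 5 h after an 08:00 dose, so laboratory testing is much less exposed than the recording.
- **The appendices were not available.** The monitor and dose logs are appendices not included in the text reviewed and may carry visit-day instructions.

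None of this places the recording within treatment. Even taking all three visit-day doses leaves at most 25% of it within 4 h of a dose, unless dosing also continues the next day.

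**Conclusion.** The concern holds as a conflict of timing. The supply, visit and monitoring text, followed as written, allows the 24-hour BP endpoint to be recorded mostly off drug: 0% of it within 4 h of a dose, or 12.5-25%, in two of the three readings that the text permits. Only continued dosing brings this to 50% (37.5-58% for 3-6 h). The likely direction of error is toward no difference, with the RR moving from about 0.67 toward 1.

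This rests on four assumptions: the effect window, which the documents do not give; nominal dose times, which are individually adjusted; the fading of drug effect outside the window; and the same arrival time and order of procedures at day 30. The arrival window and monitor fitting are described for pre-randomization testing under a heading that covers both visits. Study Objectives confirms that a post-treatment 24-hour recording is planned.

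**What to change.** 1. Reconcile the supply, visit and monitoring text, and the endpoint definition in Study Objectives, so that the post-treatment 24-hour recording lies wholly within the treatment period. One way is to schedule the monitor before the supply ends.
2. From the existing dose log, report time since last dose at the day-30 BP, CBF and cognitive tests, by arm.
3. Prespecify the percentage of readings in range within the dosed window, beside the 24-hour percentage. Define the window length in advance and apply it to both arms, since placebo subjects log dose times too.

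The cost is protocol wording, a changed fitting time for a monitor already in use, and one extra summary per subject. Only assessment timing and analysis change. How subjects are dosed is for the sponsor to settle, and no dosing rule is proposed.
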